Exploratory Endpoints	
 To demonstrate the effect of resistant potato starch (RPS) on the fecal microbiome and metabolome To determine if gnotobiotic mice colonized with the fecal microbiota of study participants models clinical response To evaluate the immunological effects of fiber supplementation in children 
 Change in peanut specific IgE and IgG4 levels Change in peanut skin prick test mean wheal diameter Change in peanut component levels
Number of Subjects	30 peanut allergic subjects will be randomized 1:1 of dietary supplementation of a fiber supplement (RPS) versus placebo
Diagnosis and Main Inclusion Criteria	
 Age 4 to 17 (inclusive) A convincing clinical history of peanut allergy Immune markers consistent with peanut allergy 
 Serum IgE to peanut of >0.35 kUA/L and a skin prick test to peanut >8mm greater than the negative saline control –or– Serum IgE to peanut of >5 kUA/L and a mean peanut wheal diameter on skin prick test 3 to 8mm greater than the negative saline control –or– Serum IgE to peanut of >14 kUA/L and mean peanut wheal diameter on skin prick test 3mm greater than the negative saline control Experience dose-limiting symptoms at or before 100mg challenge dose of peanut protein on screening double blind placebo-controlled food challenge (DBPCFC) Written informed consent from parent/guardian Written assent from subjects above the ages 4-17

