More recently, evidence expands this observation beyond infants. Identification of differentially abundant OTUs in healthy and allergic twins revealed that 84% were in the Clostridia class²⁵. These bacterial OTUs were then correlated with fecal metabolites from nonbiased metabolomic profiling, which identified another potentially protective Clostridial species in healthy twins: *R. bromii*. *R. bromii* is measurable in the feces of many (but not all) adults and is recognized as a keystone species for the degradation of type III resistant starches, like resistant potato starch (RPS)²⁶. *R. bromii* abundance in feces significantly increases upon dietary intervention with RPS^{27,28}. Individuals that do not have detectable *R. bromii* in the feces before beginning a RPS-supplemented diet consume about 40% less total starch than individuals colonized with *R. bromii*, demonstrating that this species alone is responsible for much of the total starch digestion in the colon²⁷. *R. bromii* performs the initial phases of resistant starch digestion, producing intermediate metabolites such as acetate which can then be consumed by butyrate producing bacteria. While *R. bromii* is not capable of producing butyrate itself, a recent report demonstrated that two weeks of RPS consumption by young adults was sufficient to induce detectable increases of butyrate in feces²⁹. This increase in butyrate concentration was greater in individuals who also demonstrated increased fecal abundance of *R. bromii* compared to those with no change. Butyrate concentration was also significantly correlated with changes in the abundance of *Eubacterium rectale*, a well characterized butyrate producing Clostridia²⁹. Interestingly *E. rectale* is one of the few bacterial species detectable in the microbiomes of most healthy individuals worldwide³⁰. Taken together the data suggest that *R. bromii* is a tractable biomarker, associated with a healthy microbiota and increased butyrate production, and responsive to dietary intervention. Interestingly, and in agreement with our hypothesis, the Canadian

CONFIDENTIAL

Healthy Infant Longitudinal Development birth cohort study reported that depletion of *R. bromii* early in life (3 and 12 months of age) is associated with the development of atopy and reduced genetic potential to produce butyrate³¹.

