2.2 Secondary Objective(s)

The secondary objectives of this study are:

- To determine if prebiotic therapy influences the gut microbiome/metabolome
- To determine if prebiotic therapy influences immunological markers associated with peanut allergy

3 Study Design

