3.3 Secondary Study Endpoints

The secondary endpoints are as follows:

- To determine the proportion of subjects who experience dose related GI side effects during oral immunotherapy

CONFIDENTIAL

This material is the property of the University of Chicago.
Do not disclose or use except as authorized in writing by the study PI

05.16.2023

- To determine the proportion of subjects who experience hypersensitivity reactions (other than GI) during oral immunotherapy

The exploratory endpoints are as follows:

- To demonstrate the effect of resistant potato starch (RPS) on the fecal microbiome and metabolome
- To determine if gnotobiotic mice colonized with the fecal microbiota of study participants models clinical response
- To evaluate the immunological effects of fiber supplementation in children
 - Change in peanut specific IgE and IgG4 levels
 - Change in peanut skin prick test mean wheal diameter
 - Change in peanut component levels

4 Subject Selection and Withdrawal

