7.1 Sample Size Determination

As this study is an exploratory, pilot study we will enroll 30 subjects.

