7.2 Statistical Methods

Chi-square testing (or non-parametric equivalent) will be used to compare categorical variables. Student's t-test (or non-parametric equivalent) will be used to compare continuous variables. Microbial relationships between samples will be compared using principal coordinate analysis and average-neighbor hierarchical clustering. Welch's t-test will be used to determine significant abundance differences between OTUs.

8 Safety and Adverse Events

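### The rationale rests on RPS raising faecal butyrate through R. bromii, but the plan names no lead mechanistic marker, time point or baseline adjustment, so a butyrate result would be one of many and open to post hoc selection.

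*Combined protocol and SAP*

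**What the plan says.** The mechanistic case is in section 1.1. It describes R. bromii as central to breaking down RPS and as present in many adults but not all. People without detectable R. bromii "in the feces before beginning a RPS-supplemented diet consume about 40% less total starch than individuals colonized with" it. Two weeks of RPS in young adults "was sufficient to induce detectable increases of butyrate in feces", and the rise was larger where R. bromii abundance increased. The section concludes that R. bromii "is a tractable biomarker, associated with a healthy microbiota and increased butyrate production, and responsive to dietary intervention". Section 1.4 repeats the link between RPS, R. bromii and butyrate.

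The objective in section 2.2 is "To determine if prebiotic therapy influences the gut microbiome/metabolome". The corresponding exploratory endpoint in section 3.3 is "To demonstrate the effect of resistant potato starch (RPS) on the fecal microbiome and metabolome". Neither names butyrate, short chain fatty acids, R. bromii, a visit or a contrast.

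Section 7.2 lists chi-square tests, Student's t-tests, principal coordinate analysis and clustering, and adds that Welch's t-test "will be used to determine significant abundance differences between OTUs". It states no lead marker, multiplicity rule, covariate or subgroup. Section 5.3 states no stratification factor.

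The schedule of procedures and sections 6.2 and 6.3 place a stool sample at Visit 2, before product is dispensed at Visit 3. Another is taken at Visit 4, after 30 days of product and on the day peanut oral immunotherapy (POIT) begins.

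**The concern.** The rationale makes a specific, testable prediction, and the analysis plan does not carry it through. Butyrate may well be measured within the metabolome, and R. bromii would be among the OTUs tested, so the weakness is one of prespecification and not of data collection. It has three consequences.

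- Butyrate has no more standing than any other metabolite. A positive result could be chosen after the fact, and a reader could not tell it from the false positives expected in an uncorrected screen.
- The interval from Visit 2 to Visit 4 is the only one in which RPS is taken without prior POIT dosing. It gives the cleanest view of what the supplement does, and the plan does not single it out.
- The Visit 2 value goes unused in the stated tests, although adjusting for it would sharpen a comparison of only 30 children.

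With 30 subjects, a null clinical result is quite possible. Much of the pilot's value would then lie in separating two explanations: RPS did not raise butyrate, or butyrate rose and did not help. That separation is much more convincing if the butyrate comparison was fixed in advance.

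**Working it through.** **The plan's own figure.** The sample size is given as "As this study is an exploratory, pilot study we will enroll 30 subjects", and the study summary says "30 peanut allergic subjects will be randomized 1:1", so 15 per arm. No alpha, power, effect size, SD or dropout rate is stated, so the figure cannot be reproduced. The calculations below are illustrations with all 30 subjects analysed.

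**Step 1: false positives in an uncorrected screen.** Expected false positives among m null markers tested at 5% = 0.05 × m. The documents give no m. For an assumed m of 100 the expectation is 0.05 × 100 = 5. If those tests were independent, the chance of at least one is 1 − 0.95^100 = 99.4%.

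**Step 2: one prespecified butyrate comparison, unadjusted.** Assume a true difference of d = 1 SD, two-sided alpha 0.05 and n = 15 per arm.
- Noncentrality = d × √(n/2) = 1 × √7.5 = 2.739.
- Critical t on 28 df = 2.048.
- Power from the noncentral t = 75.3%.
- The difference detectable with 80% power is about 1.06 SD.

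**Step 3: the same comparison with ANCOVA on the Visit 2 value.** The residual SD is multiplied by √(1 − ρ²), so the effective difference is d/√(1 − ρ²), now on 27 df (critical t = 2.052). The Visit 2 to Visit 4 correlation ρ is assumed.

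| ρ | effective d | noncentrality | power |
|---|---|---|---|
| 0.3 | 1/0.954 = 1.048 | 2.871 | 79% |
| 0.5 | 1/0.866 = 1.155 | 3.162 | 86% |
| 0.7 | 1/0.714 = 1.400 | 3.835 | 96% |

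**Step 4: how far non-carriage of R. bromii could dilute an effect.** Overall effect = carrier effect × [(1 − s) + s × r], where s is the share of non-carriers and r is the fraction of the effect that they keep. The documents give no s for children; 20% to 50% is assumed, as is a 30-point benefit in carriers. The value r = 0.6 assumes that benefit falls in line with the 40% lower starch use in section 1.1; r = 0 is the extreme.

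| s | r = 0.6 | r = 0 |
|---|---|---|
| 20% | 30 × 0.92 = 27.6 | 30 × 0.80 = 24 |
| 30% | 30 × 0.88 = 26.4 | 30 × 0.70 = 21 |
| 50% | 30 × 0.80 = 24 | 30 × 0.50 = 15 |

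**Step 5: what a carriage split could show.** With 20% to 50% non-carriers there are about 3 to 7 per arm. The 95% CI half-width for the RPS effect on butyrate in that group is about 1.96 × √(2/3) = 1.60 SD down to 1.96 × √(2/7) = 1.05 SD. For a carrier effect of 1.06 SD and 10% to 50% non-carriers, power for a carriage-by-arm interaction is about 11% to 29% if non-carriers do not respond at all, and about 6% to 9% if they keep 60%.

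**The case against.** The strongest reply is that this is an exploratory endpoint in a self-described pilot, that stool is collected repeatedly, and that butyrate can be compared by arm whether or not it is called the lead marker. The protocol also has a second mechanistic line in the gnotobiotic mouse endpoint. Its hypothesis reaches beyond one species, to Clostridia as a class, A. caccae, E. rectale and a barrier response. This stands in part: the mechanistic reading would be weaker, not impossible, and butyrate is the main stated pathway but not the only one. It does not answer the selection problem, which cannot be repaired after unblinding.

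A reader might infer three stronger things that the documents do not support.

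- **That children without R. bromii are non-responders.** Section 1.1 reports about 40% less starch consumed, which leaves about 60%. Its butyrate gradient follows the change in R. bromii during supplementation, not baseline carriage. The carriage statement concerns adults, while the trial enrols ages 4 to 17. Likely weaker responders is as far as the text goes, and the r = 0 column is an outer bound.
- **That a true butyrate rise would be lost to multiplicity correction.** A 1 SD effect has power of about 11% as one of 200 Bonferroni-corrected tests and 7% as one of 500. However, the plan contains neither that rule nor those counts, and its Welch tests are for OTUs, not metabolites. Under the tests as written, power at 1 SD is the 75% of Step 2. The problem that remains is false positives and selective reporting.
- **That the trial should test carriage as an effect modifier.** Step 5 shows that 30 subjects cannot support this as a confirmatory test.

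**Conclusion.** The concern holds as a gap in prespecification. The protocol has a clear mechanistic hypothesis and the samples to examine it, but no named marker, time point or baseline-adjusted comparison. As written, about 5% of null markers would be expected to reach p<0.05, with nothing to set butyrate apart from them.

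Naming one comparison removes the selection problem, and baseline adjustment raises power for an assumed 1 SD effect from about 75% to between 79% and 96%. Those figures rest on the assumed effect, on correlations of 0.3 to 0.7, on a two-sided 5% level and on 15 analysed subjects per arm; dropout would lower them. Dilution by non-carriage is a secondary matter: an assumed 30-point carrier benefit would appear as 27.6 to 24 points if non-carriers keep 60% of the effect, or 24 to 15 points if they keep none.

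The change is worth making, but the issue limits interpretation of an exploratory endpoint. The primary endpoint and the randomised clinical comparison are not invalidated.

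**What to change.** Before unblinding, amend sections 3.3 and 7.2 as follows.

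1. Name faecal butyrate at Visit 4 as the single lead mechanistic endpoint, and state that this stool is to be collected before the first POIT dose that day. Compare arms by ANCOVA with the Visit 2 value as covariate, and report the difference with a 95% CI. Fix the measurement scale (for example, whether values are log-transformed) in advance.
2. Label all other taxa and metabolites, R. bromii abundance included, as an exploratory screen. State how multiplicity will be handled there, or that p-values are unadjusted and not evidence of effect.
3. Optionally, report the RPS effect with 95% CI by R. bromii detectability in the Visit 2 stool. Set the detection threshold beforehand, assay blind to arm, and present the result as descriptive, without a confirmatory interaction test.

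No new visits or samples are needed. The costs are small: butyrate must actually be quantified within the metabolome work, which the documents do not state; the other proposed pathways remain exploratory; and the carriage groups will be very small.

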4.1 Inclusion Criteria

The following criteria are used to determine eligibility for the trial:

- Age 4 to 17 (inclusive)
- A convincing clinical history of peanut allergy
- Immune markers consistent with peanut allergy
 - Serum IgE to peanut of >0.35 kUA/L and a skin prick test to peanut >8mm greater than the negative saline control –or–
 - Serum IgE to peanut of >5 kUA/L and a mean peanut wheal diameter on skin prick test 3 to 8mm greater than the negative saline control –or–
 - Serum IgE to peanut of >14 kUA/L and mean peanut wheal diameter on skin prick test 3mm greater than the negative saline control
- Experience dose-limiting symptoms at or before 100mg challenge dose of peanut protein on screening double blind placebo-controlled food challenge (DBPCFC)
- Written informed consent from parent/guardian
- Written assent from subjects above the age of 7
- Fully vaccinated against COVID-19

4.2 Exclusion Criteria

The following are criteria used to determine eligibility for the trial:

- History of a chronic disease (other than asthma, allergic rhinitis, and atopic dermatitis) that is at significant risk of becoming unstable or requiring a change in chronic therapeutic regimen
- History of mast cell disease
- History of recurrent idiopathic or virally induced urticaria, angioedema or anaphylaxis
- Any history or presence of autoimmune, cardiovascular disease, chronic lung disease (other than asthma), malignancy, psychiatric illness, or gastrointestinal inflammatory conditions, including celiac disease, inflammatory bowel disease, eosinophilic esophagitis or other eosinophilic gastrointestinal disease
- Current participation in any other interventional study
- Subject who has undergone any type of oral immunotherapy
- Severe asthma or uncontrolled mild to moderate asthma
- Uncontrolled atopic dermatitis
- Current use of oral steroid medications
- Use of >1 bursts of oral steroid medications in the past year
- Inability to eat by mouth the fiber supplementation or placebo control and peanut flour for any reason
- Use of any therapeutic antibody (biologic medication) or any immunomodulatory medication in the past 12 month (other than a short course of oral steroids)
- Current use of any type of immunotherapy

CONFIDENTIAL

This material is the property of the University of Chicago.
Do not disclose or use except as authorized in writing by the study PI

05.16.2023

- Pregnancy or lactation
- Allergy to potato or corn
- Unwillingness to carry an epinephrine autoinjector
- Unwillingness to comply with activity restrictions during OIT or any other study procedure

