Exclusion criteria	
 • History of a chronic disease (other than asthma, allergic rhinitis, and atopic dermatitis) that is at significant risk of becoming unstable or requiring a change in chronic therapeutic regimen • History of mast cell disease • History of recurrent idiopathic or virally induced urticaria, angioedema or anaphylaxis • Any history or presence of autoimmune, cardiovascular disease, chronic lung disease (other than asthma), malignancy, psychiatric illness, or gastrointestinal inflammatory conditions, including celiac disease, inflammatory bowel disease, eosinophilic esophagitis or other eosinophilic gastrointestinal disease • Current participation in any other interventional study • Subject who has undergone any type of oral immunotherapy • Severe asthma or uncontrolled mild to moderate asthma • Uncontrolled atopic dermatitis • Current use of oral steroid medications • Use of >1 bursts of oral steroid medications in the past year • Inability to eat by mouth the fiber supplementation or placebo control and peanut flour for any reason • Use of any therapeutic antibody (biologic medication) or any immunomodulatory medication in the past 12 month (other than a short course of oral steroids) • Current use of any type of immunotherapy • Pregnancy or lactation • Allergy to potato, corn, oat or cow's milk • Unwillingness to carry an epinephrine autoinjector • Unwillingness to comply with activity restrictions during OIT or any other study procedure
Study Product and Planned Use	A prebiotic, resistant potato starch (RPS), will be given as a dietary supplement before and during oral immunotherapy to peanut
Reference therapy	Oral immunotherapy to peanut
Treatment Description	Subjects who meet inclusion criteria will be randomized 1:1 to receive either RPS or placebo. After 30 days of prebiotic therapy, subjects will start peanut oral immunotherapy (POIT) in addition to the prebiotic and continue through a prescribed course of POIT, approximately 180 days. After completion of POIT up dosing, subjects will continue on maintenance POIT plus prebiotic therapy for an additional 180 days at which time they will undergo a DBPCFC. Subjects will then stop prebiotic therapy and continue on maintenance POIT in extended observation for approximately 4 years.

CONFIDENTIAL

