DBPCFC will be conducted in accordance with PRACTALL guidelines and utilize either peanut flour (Anthony's Organic Peanut Flour) or placebo (Oat Flour; Bob's Red Mill) as previously described. Food challenges will be conducted on two separate days no more than 7 days apart and no more than 30 days prior to initial dose escalation day (for the screening food challenge). Prior to the food challenges, patients will be instructed to stop all antihistamines for 5 days prior to each challenge. All subjects will be free from asthma or atopic dermatitis flare. Asthma will be assessed by auscultation for active wheeze prior to start of the challenge and a peak expiratory flow of greater than or equal to 80% of personal best value. Atopic dermatitis flare will be assessed by investigator examination. Subjects will be admitted to the University of Chicago special procedure unit for initial dose escalation where walls are transparent glass for continuous observation by trained nursing staff. The special procedure area is located immediately above a pediatric dedicated emergency department. Subjects will be monitored on a continuous heart rate and oxygen saturation monitor throughout the procedure. Intramuscular epinephrine and oral antihistamines will be in the room with the patient prior to initiation of any doses. The patient's temperature and blood pressure will be checked before each dose. A resuscitation cart will be available within the area. A resuscitation team will be available within the hospital. Peanut flour and placebo will be mixed in either chocolate pudding and peppermint extract or applesauce and cinnamon to mask flavor and nose clips (as tolerated by the child) will be utilized during consumption to mask flavor. A second bite of vehicle will be given that does not contain challenge material followed by a sip of water prior to removal of nose clips (if nose clips can be utilized). Doses will be given every 15-20 minutes at the following doses: 1mg, 3mg, 10mg, 30mg, 100mg, 300mg (exit only), 600mg (exit only), 1000mg (exit only) peanut protein. Peanut protein constitutes half the peanut flour by weight, thus both peanut and oat flour will be administered in the following weights: 2mg, 6mg, 20mg, 60mg, 200mg, 600mg (exit only), 1200mg (exit only), 2000mg (exit only). Subjects will be monitored for at least 2 hours beyond resolution of symptoms but this period may be extended at the discretion of the investigator.

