5.1 Description

The following foods will be used:

- Fiber supplement: resistant potato starch
- Placebo: corn starch

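### The Study Summary and section 4.2 give different food-allergy exclusions, and the difference includes oat, which the trial uses as its food-challenge placebo

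*Combined protocol and SAP*

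**What the plan says.** Food-allergy exclusions appear in two places, both in current text.

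- Study Summary, exclusion criteria: "Allergy to potato, corn, oat or cow's milk".
- Section 4.2, introduced as the criteria that decide eligibility: "Allergy to potato or corn".

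Section 3.1 (Description of DBPCFC) names oat flour as the challenge placebo. It matches the placebo to the peanut flour by weight: "both peanut and oat flour will be administered in the following weights", followed by the list of weights. On the vehicle it says: "Peanut flour and placebo will be mixed in either chocolate pudding and peppermint extract or applesauce and cinnamon to mask flavor".

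Both exclusion lists also contain a general bullet: "Inability to eat by mouth the fiber supplementation or placebo control and peanut flour for any reason". Section 5.1 defines the study-food comparator as "Placebo: corn starch".

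**The concern.** Eligibility should not depend on which page of the protocol the screener has open. Here it does, for a food that the trial itself gives by mouth in rising doses to children already known to be food-allergic. Two things are at stake.

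The first is safety. A child whose oat allergy would exclude them under the Study Summary passes section 4.2 and could then be given oat flour.

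The second is the reading of the screening challenge. Section 4.1 requires a positive double-blind challenge to peanut, and the placebo day is there to show that the child does not react without peanut. A child with true oat allergy may react on that day, and the contrast that the test relies on is lost. Section 3.1 defines reactions by symptoms and gives no rule for a reaction on the placebo day.

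There is also a knock-on effect. Section 8.4.3 makes meeting an exclusion criterion during the study an individual stopping rule. While the lists differ, it is unclear whether an oat or milk allergy recognised after entry falls under that rule.

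**Working it through.** The plan states no figure to reproduce. The check compares the passages and adds up one set of doses.

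**1. The two lists side by side**

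| Allergy to | Study Summary | Section 4.2 |
|---|---|---|
| Potato | excluded | excluded |
| Corn | excluded | excluded |
| Oat | excluded | not mentioned |
| Cow's milk | excluded | not mentioned |

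The remaining exclusion bullets agree. No section says which list prevails.

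**2. Does another section 4.2 criterion cover oat?** The only candidate is the bullet on inability to eat the study foods. It pairs the placebo control with the fiber supplement, and sections 1.2 and 5.1 define that placebo as corn starch. The Study Summary carries the same bullet and still names oat and cow's milk separately. The bullet is therefore not a stated oat criterion.

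**3. When would the exposure occur?** In the Schedule of Procedures, challenges are given at visits 2 and 3, and the study arm is randomized at visit 3. The first oat day therefore falls within screening. A second would fall at visit 16 or 17 for those who reach the exit challenge.

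**4. How much oat flour?** Section 3.1 states that peanut protein is half the peanut flour by weight and that oat flour is given in the same weights as peanut flour. So oat flour = 2 × listed protein dose.

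- Screening: 2 × (1 + 3 + 10 + 30 + 100) = 2 × 144 = **288 mg**. The listed flour weights agree: 2 + 6 + 20 + 60 + 200 = 288.
- Exit: 2 × (144 + 300 + 600 + 1000) = 2 × 2044 = **4,088 mg**. The listed weights agree: 288 + 600 + 1200 + 2000 = 4,088.

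These are the totals when every listed dose is given once. Section 3.1 stops the challenge on any moderate or severe symptom, or on two or more mild ones, so a child who reacts to oat would probably receive less. The same section repeats a dose after a single mild subjective symptom; the totals exclude any repeat.

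**5. Who has an exit challenge?** Not everyone. Section 3.1 (Description of POIT) omits it when oral immunotherapy is discontinued. Section 8.4.3 limits it to those who have had six months at the maintenance dose.

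**6. Cow's milk.** The vehicle is chocolate pudding or applesauce. The milk content of the pudding is not stated, so no milk exposure can be derived.

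**The case against.** The best reply is that the protocol, read as a whole, does exclude the oat-allergic child, because the Study Summary is part of it. Nothing makes section 4.2 the governing list. A medical and allergy history is taken at visit 1, before any challenge. Challenges start at 2 mg of flour under continuous monitoring, with epinephrine in the room. All of this is correct, and it lowers the chance and severity of harm. It does not remove the contradiction: a history excludes a child only if a criterion says so, and no oat testing is listed.

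A reader might go further than the documents allow in three ways.

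- **That the primary endpoint is compromised.** One might argue that a single misclassified child moves an arm of 15 by 1/15 = 6.7 percentage points. But oat and peanut are given on separate days, and the endpoint concerns the peanut protein tolerated. A reaction to oat on the oat day does not by itself change that. The documents give neither a mechanism nor a probability of misclassification.
- **That milk in the vehicle would be scored as a peanut reaction.** This needs milk in the pudding, which is not stated, and applesauce is an alternative. The same vehicles are offered on both days, so a vehicle reaction should also show on the placebo day.
- **That every child receives the full oat amounts twice.** The stopping criteria in section 3.1 and the conditions on the exit challenge rule this out.

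**Conclusion.** The contradiction is real and needs correcting before further enrolment. Under the Study Summary a child with oat allergy is excluded; under section 4.2 the same child is eligible, and oat flour is the challenge placebo. The documents do not show that such a child is simply eligible for the trial. They show that eligibility is undetermined.

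If section 4.2 is the list applied, the exposure is up to 288 mg of oat flour at screening and, for a child who reaches the exit challenge, up to 4,088 mg. Both figures assume that all listed doses are completed once. The consequences that stand are the safety risk and a screening challenge that is hard to interpret as an entry test. Both depend on an oat-allergic child presenting. The documents give no prevalence, and the number affected may be zero. No consequence is shown for cow's milk or for the primary endpoint.

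**What to change.** Reconcile the Study Summary and section 4.2 into one identical exclusion list before any further enrolment. In doing so, check the list against the foods that the trial itself administers, including the oat-flour placebo, and establish whether the pudding vehicle contains milk. Which allergies belong on the list is for the investigators to settle. If any subjects are already enrolled, compare their recorded allergy histories with the reconciled list.

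The cost is a one-line amendment and a chart check. If the reconciled list is the longer one, a few otherwise eligible children with several food allergies may be excluded.
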